17.1 Adverse Events

The severity of adverse events will be graded using the NCI-CTCAE, version 4.0 except where CTCAE grades are missing. No imputation of missing grades will be performed. Adverse events will be coded according to the latest available version of MedDRA.

- **Treatment Emergent Adverse Event:** TEAEs are those events with onset dates occurring during the on-treatment period for the first time, or if the worsening of an event is during the on-treatment period as defined in [Section 11](#).
- **Related Adverse Event:** adverse events with relationship to study treatment (relationship with study treatment = related) reported by the investigator and those of unknown relationship (i.e. no answer to the question “Relationship with study treatment”).
- **Serious Adverse Event (SAE):** serious adverse events (as recorded on the AE eCRF page, serious adverse event = yes).
- **Adverse Event Leading to Treatment Discontinuation:** adverse events leading to permanent discontinuation of study treatment (as recorded on the AE eCRF page, action taken with study treatment = drug withdrawn).
- **Adverse Event Leading to Death:** adverse event leading to death (as recorded on the AE eCRF page, outcome = fatal or toxicity grade = 5).
- **Infusion Related Reaction (IRR):** IRRs are identified by 3 PTs (infusion related reaction, drug hypersensitivity, anaphylactic reaction) with onset on study drug dosing date (not prior to infusion of study drug) or the day following study drug infusion.
- **Immune Related Adverse Event (irAE):** irAEs are identified according to a pre-specified search list of MedDRA PTs, documented in a version-controlled repository maintained by the Sponsor and finalized for analysis prior to database lock.

AEs will be summarized using the MedDRA PT as event category and MedDRA primary SOC as summary category. All AE tables will be restricted to TEAEs unless otherwise specified.

Each subject will be counted only once within each PT or SOC and recording period. If a subject experiences more than one AE within a PT or SOC for the same recording period, only the AE with the strongest relationship or the worst severity, as appropriate, will be included in the summaries of relationship and severity. AEs with missing classifications regarding relationship to study treatment and start date greater or equal to start of study treatment will be considered as related to study treatment. AEs with missing toxicity grade will be counted into ‘any grade’ in the summarization by toxicity grade.

The AE tables will include the number and percentage of subjects with at least one TEAE, by MedDRA primary SOC (sorted by decreasing SOC frequencies in the overall column) and by PT (sorted by decreasing PT frequencies in overall column within SOC), unless otherwise stated.

17.1.1 All Adverse Events

All adverse events will be tabulated in the following tables by dose level and overall.

-
- The overall summary of AEs table will include the following variables:
 - TEAEs
 - TEAEs, grade ≥ 3
 - Related TEAEs
 - Related TEAEs, grade ≥ 3
 - TEAEs leading to permanent treatment discontinuation
 - Related TEAEs leading to permanent treatment discontinuation
 - Serious TEAEs
 - Related serious TEAEs
 - TEAEs leading to death
 - Related TEAEs leading to death
 - Treatment emergent irAEs
 - Related treatment emergent irAEs
 - Treatment emergent IRRs
 - Related treatment emergent IRRs
 - Incidence of TEAEs by SOC, PT, and worst grade
 - Incidence of related TEAEs by SOC, PT, and worst grade
 - Incidence of TEAEs by SOC and PT: displaying in separate columns All TEAEs / Related TEAEs / Grade ≥ 3 TEAEs / Related Grade ≥ 3 TEAEs
 - Incidence of TEAEs leading to death by SOC and PT
 - Incidence of related TEAEs leading to death by SOC and PT
 - Incidence of non-serious TEAEs by SOC and PT

Listing of AEs including all relevant information such as AE SOC/PT, start/stop date, toxicity grade, relationship to the study treatment, action taken with study treatment, and outcome etc., will be provided. A separate listing of TEAEs started or worsened after on-treatment period will also be provided.

17.1.2 Adverse Events Leading to Treatment Discontinuation

Following summary tables will be produced:

- Incidence of TEAEs leading to permanent treatment discontinuation by SOC and PT
- Incidence of related TEAEs leading to permanent treatment discontinuation by SOC and PT

The listing of AEs leading to permanent treatment discontinuation will also be provided with the relevant information such as AE SOC/PT, start/stop date, toxicity grade, relationship to the study treatment, and outcome etc.

17.1.3 Serious Adverse Events

Following summary tables will be produced:

- Incidence of serious TEAEs by SOC and PT
- Incidence of related serious TEAEs by SOC and PT

The listings of SAEs will also be provided with the relevant information such as AE SOC/PT, start/stop date, toxicity grade, relationship to the study treatment, action taken with study treatment, and outcome etc.

17.1.4 Infusion Related Reactions

IRRs will be summarized by the follow variables:

- Number of subjects with at least one event by the worst toxicity grade (grade 1/ grade 2/ grade 3/ grade 4/ grade 5/ missing grade)
- Number of subjects with IRR leading to permanent treatment discontinuation
- Time related to first onset (infusion 1/ infusion 2/ infusion 3/ infusion 4 or later). The events should be assigned to the actual drug infusions that the subject received, not to the planned dates. An IRR is assigned to a drug infusion if its onset is at the same date (but not before dosing) or the following day of drug infusion.
- Number of subjects with at least one event by the worst toxicity grade that occurred in the presence of premedication (grade 1/ grade 2/ grade 3/ grade 4/ grade 5/ missing grade). The denominator will be the number of subjects with at least one dose administered in the presence of premedication. The maximum toxicity will be derived among those IRRs that occurred in the presence of premedication.
- Number of subjects with at least one event by the worst toxicity grade that occurred in the absence of premedication (grade 1/ grade 2/ grade 3/ grade 4/ grade 5/ missing grade). The denominator will be the number of subjects with at least one dose administered in the absence of premedication. The maximum toxicity will be derived among those IRRs that occurred in the absence of premedication.

The listing of IRRs will be provided with the relevant information such as AE SOC/PT, start/stop date, toxicity grade, relationship to the study treatment, action taken with study treatment, outcome, premedication, and study medication batch ID etc.

17.1.5 Immune Related Adverse Events

irAEs will be summarized using the following variables:

-
- The overall summary of treatment emergent irAEs will include the following categories:
 - irAEs
 - Related irAEs
 - Grade ≥ 3 irAE
 - Related grade ≥ 3 irAE
 - irAEs leading to permanent treatment discontinuation
 - Related irAEs leading to permanent treatment discontinuation
 - Serious irAEs
 - Related serious irAEs
 - irAEs leading to death
 - Related irAEs leading to death
 - Incidence of treatment emergent irAEs by SOC and PT.

A listing containing all the PTs used to identify irAEs and a listing containing all the irAEs in the study will be generated as well.

17.1.6 Subgroup Analysis of Adverse Events

Subgroup analyses of AEs (TEAEs, irAEs, SAEs, IRRs) based on immunogenicity responses will be performed using summary statistics for qualitative comparison only. The number and percentage of subjects with at least one TEAE, irAE, SAE, or IRR will be compared between HAHA ever positive versus HAHA never positive subjects, and between subjects with treatment emergent immunogenicity response and the rest of the subjects.

17.2 Deaths

All deaths will be tabulated and listed for SAF analysis set by dose level and overall. The deaths table will include the following information:

- Number of subjects who died
 - Primary reason for death
 - Disease progression
 - Adverse event related to study treatment
 - Adverse event not related to study treatment
 - Other
 - Unknown

- Number of subjects who died within 30 days of the last study treatment administration
 - Primary reason for death
 - Disease progression
 - Adverse event related to study treatment
 - Adverse event not related to study treatment
 - Other
 - Unknown

The listing of deaths will be provided with all the relevant information such as death date and reason for death. The death data will be ascertained from the dedicated Report of Death eCRF form.

17.3 Clinical Laboratory Evaluation

Laboratory abnormalities are classified according to NCI-CTCAE toxicity grading version 4.0 or based on normal ranges collected from laboratories. The toxicity grading is only related to the lab values itself and does not respect the non-numeric information as described in the CTC grading definition. CTCAE gradable parameters and associated toxicities are listed in Table 6.

Table 6 CTCAE Gradable Parameters and Associated Toxicities

Panel	Parameter (test)	Low direction toxicity	High direction toxicity
Hematology	Hemoglobin (HB)	anemia	hemoglobin increased
	Leukocytes	white blood cell decreased	
	Lymphocytes	lymphocyte count decreased	lymphocyte count increased
	Neutrophils/ absolute neutrophils count (ANC)	neutrophil count decreased	
	Platelet count (PLT)	platelet count decreased	
Chemistry	Albumin	hypoalbuminemia	
	Alkaline phosphatase (ALP)		alkaline phosphatase increased
	Alanine aminotransferase (ALT)		ALT increased
	Amylase		serum amylase increased
	Aspartate aminotransferase (AST)		AST increased
	Bilirubin (total)		blood bilirubin increased
	Cholesterol		cholesterol high
	Creatinine		creatinine increased
	Creatinine clearance	chronic kidney disease	
	Creatine kinase (CPK)		CPK increased
	Potassium	hypokalemia	hyperkalemia
	Sodium	hyponatremia	hypernatremia
	Magnesium	hypomagnesemia	hypermagnesemia
	Calcium	hypocalcemia	hypercalcemia

	Glucose	hypoglycemia	hyperglycemia
	Gamma glutamyl transferase (GGT)		GGT increased
	Lipase		lipase increased
	Phosphates	hypophosphatemia	
	Triglycerides		hypertriglyceridemia
Coagulation	Prothrombin time INR		INR increased
	Activated Partial thromboplastin time (aPTT)		aPTT prolonged

Grade 1 and 2 hypoglycemia/ hyperglycemia are based on fasting glucose, they will not be graded for this study because blood samples are taken from non-fasted subjects.

For calcium, CTCAE grading is based on corrected calcium and ionized calcium (CALCIO), if available. Corrected calcium is calculated from albumin and calcium as follows

$$\text{Corrected calcium (mg/dL)} = \text{Calcium (mg/dL)} - 0.8 [\text{Albumin (g/dL)} - 4].$$

Chronic kidney disease will be graded based on estimated creatinine clearance rate (eCcr, ml/min), which is derived using Cockcroft-Gault formula:

$$eCcr = \frac{(140 - \text{Age}) \times \text{Weight}(kg) \times \text{Constant}}{\text{Serum Creatinine } (\mu\text{mol/L})}$$

where the constant is 1.23 for men and 1.04 for women.

The following are non-CTCAE gradable parameters collected in this study, their abnormalities are assessed as low, high, normal based on the comparison of observed values with normal ranges.

- Hematology: hematocrit, red blood cell (RBC), reticulocytes, mean corpuscular hemoglobin (MCH), mean corpuscular volume (MCV), mean corpuscular hemoglobin concentration (MCHC).
- Serum Chemistry: chlorine, C-reactive protein, lactate dehydrogenase (LDH), total protein, total urea, uric acid.
- Hormone: adrenocorticotrophic hormone (ACTH), anti-nuclear antibody (ANA), anti-neutrophil cytoplasmic antibody (ANCA), rheumatoid factor (RF), free thyroxine (Free T4), thyroid-stimulating hormone (TSH).

Laboratory abnormalities will be summarized using the worst grade during the on-treatment period. For these parameters which are graded with two toxicities such as potassium (hypokalemia/hyperkalemia), the toxicities will be summarized separately. Low direction toxicity (eg. hypokalemia) grades at baseline and post-baseline will be set to 0 when the variables are derived for summarizing high direction toxicity (e.g. hyperkalemia), and vice versa.

The change and percent change from baseline will be derived for parameters with numeric results.

17.3.1 Hematology, Chemistry, and Hormone Parameters

CTCAE gradable parameters

The laboratory toxicities will be tabulated by the worst on-treatment CTCAE grade or the shift of CTCAE grade from baseline to worst grade during on-treatment period using descriptive statistics (count and percentage). The highest CTCAE grade during the on-treatment period is considered as the worst grade for the summary.

- The worst grade during the on-treatment period will be summarized considering only patients with post baseline laboratory samples: Laboratory tests by NCI-CTCAE grade (0, 1, 2, 3, 4, and missing).
- The shift table will summarize baseline CTCAE grade vs. the worst on-treatment CTCAE grade (grade = 0, 1, 2, 3, 4, missing).

Non-CTCAE gradable parameters

Hematology, chemistry, and hormone evaluations which can't be graded per CTCAE will be summarized as:

- Shift from baseline value (low, normal, high) to above normal during on-treatment period
- Shift from baseline value (low, normal, high) to below normal during on-treatment period

Quantitative data will also be examined for trends using descriptive statistics (n, missing, mean, SD, median, Q1, Q3, minimum, and maximum) of actual values, absolute changes and percent changes from baseline to each visit over time. This summarization will apply to hematology and chemistry parameters with numeric results assessed at baseline, post-baseline, discontinuation, end of treatment, and/or safety follow-up visits based on visit windows specified in [Section 11](#).

The listings (hematology, chemistry, and hormone) will include all the laboratory parameters as available in the database with the relevant information such as visit, assessment date, parameter, value, normal ranges etc. Listings will be sorted by subject identifier, group variable, parameter, assessment date or visit.

Liver function parameters

ALT, AST, ALP, and total bilirubin are used individually or together to assess possible drug induced liver toxicity. The ratio of test result over upper limit of normal (ULN) for individual test or combined tests will be calculated and classified for these parameters during the on-treatment period.

Summary of liver function tests will include the following categories. The number and percentage of subjects with each of the following during the on-treatment period will be summarized by dose level and overall:

- $AST \geq 3*ULN / \geq 5*ULN / \geq 10*ULN / \geq 20*ULN$.
- $ALT \geq 3*ULN / \geq 5*ULN / \geq 10*ULN / \geq 20*ULN$.
- $(ALT \text{ or } AST) \geq 3 \times ULN / \geq 5 \times ULN / \geq 10 \times ULN / \geq 20 \times ULN$

-
- Total bilirubin $\geq 2 \times \text{ULN}$.
 - Concurrent ALT $\geq 3 \times \text{ULN}$ and TBILI $\geq 2 \times \text{ULN}$
 - Concurrent AST $\geq 3 \times \text{ULN}$ and TBILI $\geq 2 \times \text{ULN}$
 - (ALT or AST) $\geq 3 \times \text{ULN}$ concurrently with total bilirubin $\geq 2 \times \text{ULN}$.
 - (ALT or AST) $\geq 3 \times \text{ULN}$ concurrently with total bilirubin $\geq 2 \times \text{ULN}$ and ALP $> 2 \times \text{ULN}$.
 - (ALT or AST) $\geq 3 \times \text{ULN}$ concurrently with total bilirubin $\geq 2 \times \text{ULN}$ and (ALP $\leq 2 \times \text{ULN}$ or missing).

Concurrent measurements are those occurring on the same date.

Categories will be cumulative, i.e. a subject with an elevation of AST $\geq 10 \times \text{ULN}$ will also appear in the categories $\geq 5 \times \text{ULN}$ and $\geq 3 \times \text{ULN}$. Liver function elevation and possible Hy's Law cases will be summarized using frequency and percentage by dose level and overall.

An evaluation of Drug-Induced Serious Hepatotoxicity (eDISH) plot will also be created to graphically display

- peak serum ALT(/ULN) vs. concurrent total bilirubin (/ULN) including reference lines at ALT $> 3 \times \text{ULN}$ and total bilirubin $> 2 \times \text{ULN}$.
- peak serum AST(/ULN) vs. concurrent total bilirubin (/ULN).

Listing of subjects with ALT or AST $\geq 3 \times \text{ULN}$ or total bilirubin $\geq 2 \times \text{ULN}$ will include variables subject identifier, visit, date of collection, study day, parameter (ALT, AST, ALP, total bilirubin), result, unit, result/ULN, CTCAE grade.

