
Grade 1 Grade 1 AST or ALT > ULN to 3.0 x ULN and / or total bilirubin > ULN to 1.5 x ULN
	
Continue avelumab therapy
	
Continue liver function monitoring If worsens: Treat as Grade 2 or 3 to 4

Grade 2 AST or ALT > 3.0 to ≤ 5 x ULN and / or total bilirubin > 1.5 to ≤ 3 x ULN
	
Delay avelumab therapy Increase frequency of monitoring to every 3 days
	
If returns to baseline: Resume routine monitoring, resume avelumab therapy If elevations persist > 5 to 7 days or worsen: 0.5 to 1 mg/kg/day methylprednisolone or oral equivalent and when LFT returns to Grade 1 or Baseline, taper steroids over at least 1 month, consider prophylactic antibiotics for opportunistic infections, and resume avelumab therapy

Grade 3 to 4 AST or ALT > 5 x ULN and / or total bilirubin > 3 x ULN
	
Discontinue avelumab therapy Increase frequency of monitoring to every 1 to 2 days 1.0 to 2.0 mg/kg/day methylprednisolone i.v. or i.v. equivalent Add prophylactic antibiotics for opportunistic infections Consult gastroenterologist Consider obtaining MRI/CT scan of liver and liver biopsy if clinically warranted
	
If returns to Grade 2: Taper steroids over at least 1 month If does not improve in > 3 to 5 days, worsens or rebounds: Add mycophenolate mofetil 1 gram (g) twice daily If no response within an additional 3 to 5 days, consider other immunosuppressants per local guidelines

Cardiac irAEs		
Myocarditis	Management	Follow-up
New onset of cardiac signs or symptoms and / or new laboratory cardiac biomarker elevations (e.g. troponin, CK-MB, BNP) or cardiac imaging abnormalities suggestive of myocarditis	
Withhold avelumab therapy.
 
Hospitalize.
 
In the presence of life threatening cardiac decompensation, consider transfer to a facility experienced in advanced heart failure and arrhythmia management.
 
Cardiology consult to establish etiology and rule out immune-mediated myocarditis.
 
Guideline based supportive treatment as per cardiology consult.^a
 
Consider myocardial biopsy if recommended per cardiology consult.
	
If symptoms improve and immune-mediated etiology is ruled out, re-start avelumab therapy.
 
If symptoms do not improve/worsen, viral myocarditis is excluded, and immune-mediated etiology is suspected or confirmed following cardiology consult, manage as immune-mediated myocarditis.

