 - On-treatment period is defined as the time from the first dose of study treatment to the last dose date + 30 days, or the earliest date of subsequent anti-cancer drug therapy – 1 day, whichever occurs first. If the earliest date of subsequent anti-cancer drug therapy is a partial date and only day is missing, it will be imputed as the last day of the month. If both day and month are missing, no imputation should be performed. The imputed date will be used for defining on-treatment period as well as confirming immune-related progressive disease (irPD).
 - All statistical analyses will be performed using SAS® Version 9.1.3 or higher.
 - There will be no difference between scheduled and un-scheduled visits except for by-visit analysis of safety data and baseline derivation.
 - The assignments of visit windows are described in Table 1 for the purpose of by-visit analyses of safety data:
 - Baseline will be derived as described above.
 - No visit windowing will be performed at discontinuation, end of treatment, or safety follow-up visits for laboratory, vital sign, and ECG data, and 2hr post dose assessment on Week 1 Day 1 for ECG data. Instead, the earliest non-missing observation among the unscheduled or scheduled assessments for each visit (discontinuation, end of treatment, or safety follow-up) will be used for the analysis. For 2hr post dose assessment on Week 1 Day 1 ECG data, the earliest non-missing observation on Week 1 Day 1 will be used for the analysis.
 - Scheduled and unscheduled assessments are included for visit windowing. Assessments on or after re-initiation of treatment are not be included for visit windowing.
 - If there are multiple assessments for any specified visit and some of them are from scheduled visits, the assessment from scheduled visit with the closest distance to the planned study day will be used for analysis.
 - If there are multiple assessments for any specified visit and none of them are from scheduled visits, the assessment with the closest distance to the planned study day will be used for analysis.

- If there are two or more unscheduled assessments with same distance to the planned study day such as (-1/+1 day), the assessment prior to the planned study day such as -1 day will be used for windowing.

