- $ALT \geq 3*ULN / \geq 5*ULN / \geq 10*ULN / \geq 20*ULN$.
- $(ALT \text{ or } AST) \geq 3*ULN / \geq 5*ULN / \geq 10*ULN / \geq 20*ULN$
- Total bilirubin $\geq 2*ULN$
- Concurrent $ALT \geq 3*ULN$ and $TBILI \geq 2*ULN$
- Concurrent $AST \geq 3*ULN$ and $TBILI \geq 2*ULN$
- $(ALT \text{ or } AST) \geq 3*ULN$ concurrently with total bilirubin $\geq 2*ULN$.
- $(ALT \text{ or } AST) \geq 3*ULN$ concurrently with total bilirubin $\geq 2*ULN$ and $ALP > 2*ULN$.
- $(ALT \text{ or } AST) \geq 3*ULN$ concurrently with total bilirubin $\geq 2*ULN$ and $(ALP \leq 2*ULN \text{ or missing})$.

Concurrent measurements are those occurring on the same date.

Categories will be cumulative, i.e a subject with an elevation of $AST \geq 10*ULN$ will also appear in the categories $\geq 5*ULN$ and $\geq 3*ULN$. Liver function elevation and possible Hy's Law cases will be summarized using frequency and percentage by cohort.

An evaluation of Drug-Induced Serious Hepatotoxicity (eDISH) plot will also be created to graphically display

- peak serum ALT(/ULN) vs. peak total bilirubin (/ULN) including reference lines at $ALT \geq 3*ULN$ and total bilirubin $\geq 2*ULN$.
- peak serum AST(/ULN) vs. peak total bilirubin (/ULN).

Listing of subjects with $ALT \text{ or } AST \geq 3*ULN$ or total bilirubin $\geq 2*ULN$ will include variables subject identifier, visit, date of collection, study day, parameter (ALT, AST, ALP, total bilirubin), result, unit, result/ULN, CTCAE grade.

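### The dose-escalation eDISH plots pair peak ALT or AST with same-date bilirubin, so a subject counted in the SAP's own combined liver row can be plotted outside the Hy's Law region

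*SAP*

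**What the plan says.** Both SAPs have a section 17.3.1 with a part on liver function. The dose-escalation SAP gives the purpose: "ALT, AST, ALP, and total bilirubin are used individually or together to assess possible drug induced liver toxicity". It plans three kinds of output.

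- **Table rows.** There are single-test rows (for example ALT, AST or either at >=3xULN and above; bilirubin >=2xULN). There are also combined rows joining ALT and/or AST >=3xULN with bilirubin >=2xULN, two of them split by ALP. Every combined row is concurrent: "Concurrent measurements are those occurring on the same date". Any such date in the on-treatment period counts, not only the date of the peak.
- **eDISH plots.** One shows "peak serum ALT(/ULN) vs. concurrent total bilirubin (/ULN) including reference lines", with lines at 3xULN for ALT and 2xULN for bilirubin. The other shows "peak serum AST(/ULN) vs. concurrent total bilirubin (/ULN"), with no lines stated.
- **A listing** of subjects with ALT or AST >=3xULN or bilirubin >=2xULN, which "will include variables subject identifier, visit, date of collection, study day, parameter (ALT, AST, ALP, total bilirubin), result, unit, result/ULN, CTCAE grade".

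The expansion SAP keeps the same rows, the same definition of concurrent and the same listing. Its ALT plot is different: "peak serum ALT(/ULN) vs. peak total bilirubin (/ULN) including reference lines". Its AST plot is also peak against peak.

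**The concern.** An eDISH plot is meant to show at a glance which subjects had both a marked transaminase rise and a marked bilirubin rise. If bilirubin lags the enzymes, reading it on the day of the enzyme peak gives a low value, and the point falls in the region of enzyme elevation alone. The combined row looks at every date, so the table and the plot in one report can then disagree about the same subject.

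A second, separate gap lies in the rows of both SAPs. If ALT and AST have both dropped below 3xULN before bilirubin reaches 2xULN, no date satisfies a combined row. In dose escalation such a subject is flagged by neither joint display. In expansion the peak-against-peak plot still flags the subject.

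At stake is how readily a possible Hy's Law case is recognised in a safety report.

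**Working it through.** The plan states no figure to reproduce, so the check applies the written rules to assumed subjects.

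**Rules** (all values in xULN):

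- Combined row, both SAPs: counted if on some date *d*, ALT(*d*) or AST(*d*) >=3 and bilirubin(*d*) >=2.
- Escalation point: (peak enzyme, bilirubin on the date of that peak).
- Expansion point: (peak enzyme, peak bilirubin).
- Region: enzyme beyond 3 and bilirubin beyond 2. I apply the same limits to the AST plots, for which the SAPs state no lines. The escalation ALT plot draws its lines at > and the table uses >=; no assumed value lies on a limit, so this does not affect the results.

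The liver tests are drawn as one panel (Protocol Appendix I, core serum chemistry), so same-date pairs normally exist. The issue is timing, not missing pairs.

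**Assumed subjects.** A to C have draws every 2 days; D and E use scheduled visit days.

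| Series | Days | ALT | AST | Bilirubin |
|---|---|---|---|---|
| A | 15, 17, 19, 21, 23 | 6.0, 4.5, 3.2, 2.6, 2.1 | 5.0, 3.8, 2.7, 2.1, 1.7 | 1.2, 1.5, 1.8, 2.3, 2.6 |
| B | 15, 17, 19, 21, 23 | 6.0, 5.2, 4.3, 3.5, 2.7 | 5.0, 4.3, 3.6, 2.9, 2.2 | 1.2, 1.7, 2.2, 2.8, 2.4 |
| C | 15, 17, 19, 21, 23 | as B | 3.2, 3.7, 4.0, 3.4, 2.6 | as B |
| D | 29, 43, 57 | 8, 4, 1.5 | 7, 3.5, 1.2 | 1.4, 2.6, 1.8 |
| E | 29, 43, 57 | 8, 2.5, 1.2 | 7, 2.2, 1.0 | 1.4, 2.6, 1.5 |

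**Results**

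| Series | Combined row | Escalation ALT; AST point | Peak-against-peak ALT; AST point |
|---|---|---|---|
| A | no | (6.0, 1.2) out; (5.0, 1.2) out | (6.0, 2.6) in; (5.0, 2.6) in |
| B | yes, Days 19 and 21 | (6.0, 1.2) out; (5.0, 1.2) out | (6.0, 2.8) in; (5.0, 2.8) in |
| C | yes, Days 19 and 21 | (6.0, 1.2) out; (4.0, 2.2) in | (6.0, 2.8) in; (4.0, 2.8) in |
| D | yes, Day 43 | (8, 1.4) out; (7, 1.4) out | (8, 2.6) in; (7, 2.6) in |
| E | no | (8, 1.4) out; (7, 1.4) out | (8, 2.6) in; (7, 2.6) in |

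- **B and D** are the main finding: the table counts the subject and both escalation plots place the point outside the region.
- **C** is its limit. If one enzyme peaks on a date when bilirubin is already raised, that enzyme's plot shows the case.
- **A and E** are the second gap. The last enzyme value >=3 precedes the first bilirubin >=2 by 21 - 19 = 2 days in A and by 43 - 29 = 14 days in E.
- **All five** are in the ALT, AST and bilirubin single-test rows and in the listing.

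Peak-against-peak removes the conflict in B and D by construction. If some date has an enzyme >=3 with bilirubin >=2, then that enzyme's peak is >=3 and peak bilirubin is >=2. Every subject in a combined row therefore lies in the region on at least one plot, provided the lines are read as >=.

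**The case against.** The strongest reply is that same-date pairing is explicit and pre-specified, and that peak-against-peak has a fault of its own. It sets no time limit, so it can join an early enzyme peak to bilirubin raised much later by progression. That matters here, because Protocol 5.3.1 admits dose-escalation subjects with liver metastases at AST and ALT up to 5xULN. This stands as a reason to check the plotted points, but not as a reason to keep a plot that can contradict its own table. The sponsor chose peak-against-peak in the expansion SAP.

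A reader might infer that the plots leave such subjects out, or that the cases disappear from the report. The documents do not support either reading. The subject is plotted, in B beyond the 3xULN ALT line, and only the region is wrong. The single-test rows and the listing retain the case. A treatment-related Grade 3 enzyme rise also calls for discontinuation (Protocol 5.1.7.2), and laboratory findings that lead to discontinuation are reportable as adverse events (Protocol 7.4.1.1). The case would therefore probably reach the adverse event tables as well.

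Dense testing should make series like A and E uncommon. Current Protocol Table 6.2 says, for Grade 3 to 4 liver tests, "Increase frequency of monitoring to every 1 to 2 days", and unscheduled values enter these rows: "There will be no difference between scheduled and un-scheduled visits except for by-visit analysis of safety data and baseline derivation" (dose-escalation SAP section 11). However, that table covers immune-related events in a later amendment than Amendment 12, to which the escalation SAP refers. It is not shown to have applied to these subjects, so it cannot be used to bound the frequency.

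**Conclusion.** The point holds as a minor, cheap improvement centred on the two dose-escalation plots. It rests on the SAP's own definition of concurrent and needs only that bilirubin first reaches 2xULN after both enzyme peaks. For AST it also assumes the 3xULN and 2xULN limits. The five series show that the conflict can occur; they say nothing about how often. The frequency is unknown and probably low, in a phase that the SAP sizes at 18 to 60 subjects.

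The row gap in both SAPs is real but weaker. The documents set no time window and do not call for a lagged row, and in expansion the plots already show these cases. It would be wrong to infer that the expansion plots share the fault, or that the dose conclusions are in doubt. DLTs are graded, treatment-related events confirmed by the safety monitoring committee (Protocol 5.1.4.3), and do not depend on these displays. No endpoint or dose decision changes.

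**What to change.** 1. **Dose-escalation SAP 17.3.1.** Plot peak ALT and peak AST each against peak bilirubin, as the expansion SAP does. Draw the 3xULN and 2xULN lines on both plots and read them as >= to match the table.
2. **Check each point in the region against the dated listing**, and note the interval between the enzyme and bilirubin values, since the pairing has no time limit.
3. **Optional, both SAPs.** Keep the same-date rows and add one row: ALT or AST >=3xULN with bilirubin >=2xULN on the same date or within a pre-stated window afterwards, both in the on-treatment period. A window of 2 days or more would count A; one of 14 days or more would also count E. Thirty days is only an example and would have to be justified. Do not add windowed ALP-split rows unless the date of the ALP value is also defined.

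The cost is two redrawn plots and at most one extra row, from data already collected. Protocol 3.5.1 describes the dose-escalation safety analysis as complete, so there the output would be reported as unplanned, as section 5 of that SAP provides. The downside is a few extra candidate cases for medical review, some of them due to liver metastases or progression.
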